**International Centre for Diarrhoeal Disease Research, Bangladesh**  
**Fish intervention on vitamin A status in children – a study in Mirpur**

**Household Socio-economic Form (4)**

Household mapping ID#

Camp code

**1. Which source of water is used for:**

- |                            |  |   |
|----------------------------|--|---|
| a. Drinking         | Municipality supply = 1
Tube well = 3 | Own arrangement by plastic pipe = 2
Well = 4      Others = 5 _____ |
| b. Cooking          | Municipality supply = 1
Tube well = 3 | Own arrangement by plastic pipe = 2
Well = 4      Others = 5 _____ |
| c. Washing utensils | Municipality supply = 1
Tube well = 3 | Own arrangement by plastic pipe = 2
Well = 4      Others = 5 _____ |
| d. Bathing          | Municipality supply = 1
Tube well = 3 | Own arrangement by plastic pipe = 2
Well = 4      Others = 5 _____ |
| e. Others           | Municipality supply = 1
Tube well = 3 | Own arrangement by plastic pipe = 2
Well = 4      Others = 5 _____ |

**2. Do you store water for each of the following purposes:**

- |                            |         |        |
|----------------------------|---------|--------|
| a. Drinking         | Yes = 1 | No = 2 |
| b. Cooking          | Yes = 1 | No = 2 |
| c. Washing utensils | Yes = 1 | No = 2 |
| d. Bathing          | Yes = 1 | No = 2 |
| e. Others           | Yes = 1 | No = 2 |

**3A. Which type of pot is used to store the water:**

- |                         |         |        |                            |         |        |
|-------------------------|---------|--------|----------------------------|---------|--------|
| 1. Small bucket  | Yes = 1 | No = 2 | 5. Small container  | Yes = 1 | No = 2 |
| 2. Medium bucket | Yes = 1 | No = 2 | 6. Medium container | Yes = 1 | No = 2 |
| 3. Big bucket    | Yes = 1 | No = 2 | 7. Big container    | Yes = 1 | No = 2 |
| 4. Jug           | Yes = 1 | No = 2 | 8. Other _____      | Yes = 1 | No = 2 |

## Household Socio-economic Form (5)

Household mapping ID#  Camp code

3B. How many times during 24 hours is water being collected (for all purposes)

4. What is the self-made waterline near to:

Latrine = 1    Drain = 2    Other = 3    N.A. = 4

5. Which type of latrine is used for each of the following age groups:

a.	Males (>7 years)	No fixed place = 1	Open = 2	Sanitary = 3	Pit = 4
b.	Females (>7 years)	No fixed place = 1	Open = 2	Sanitary = 3	Pit = 4
c.	5-7 years children	No fixed place = 1	Open = 2	Sanitary = 3	Pit = 4
d.	3-4 years children	No fixed place = 1	Open = 2	Sanitary = 3	Pit = 4
e.	< 3 years children	No fixed place = 1	Open = 2	Sanitary = 3	Pit = 4

6. Is the household using an individual or shared latrine:

Individual = 1    Shared = 2

7. Using slippers to the latrine:

a. Does the study child use slippers to the latrine

Study child ID#  Yes = 1    No = 2

Study child ID#  Yes = 1    No = 2

Study child ID#  Yes = 1    No = 2

b. Total members in the household

c. Number of members who use slippers to the latrine

## Household Socio-economic Form (6)

Household mapping ID#            Camp code

8. What kind of hand washing practice is being used for each of the following purposes:

Purpose	Type of agents*	How*	Source of water*
a. Before food preparation			
b. Before eating			
c. After defecating			
d. Cleaning child's bottom			
e. Other			

\***Type of agent**      No = 0      Water = 1      Mud = 2      Ash = 3      Soap = 4  
 Other = 5 \_\_\_\_\_

\***How**                      No = 0      Left hand = 1      Right hand = 2      Both hand = 3

\***Source**                      Municipality supply = 1      Own arrangement by plastic pipe = 2  
 Tube well = 3                      Well = 4  
 Others = 5 \_\_\_\_\_

9A. Is the drinking water container being covered      Yes = 1      No = 2

9B. Is the raw food being covered      Yes = 1      No = 2

9C. Is the cooked food/ curries being covered      Yes = 1      No = 2

10. Construction of the house:

a. What is the wall made of  
 Pacca = 1                      Bamboo = 2                      Tin = 3                      Hardboard/Polythene=4  
 Katcha/Mud = 5                      Brick made = 6                      Thatched = 7                      Corrugated tin = 8

b. What is the floor made of  
 Pacca = 1                      Bamboo = 2                      Tin = 3                      Hardboard/Polythene=4  
 Katcha/Mud = 5                      Brick made = 6                      Thatched = 7                      Corrugated tin = 8

c. What is the roof made of  
 Pacca = 1                      Bamboo = 2                      Tin = 3                      Hardboard/Polythene=4  
 Katcha/Mud = 5                      Brick made = 6                      Thatched = 7                      Corrugated tin = 8

d. Is the bedroom and kitchen attached?      Yes = 1      No = 2

## Household Socio-economic Form (7)

Household mapping ID#:  Camp code:

11. Number of windows in dwelling house:

12. Number of rooms in dwelling house:

13. Open drain around the house:

a. Is there an open drain beside the bedroom Yes = 1 No = 2

b. Is there an open drain beside the kitchen Yes = 1 No = 2

14. Are domestic/wild animals presence in the household:

Goat = 1 Chicken = 2 Cat = 3 Dog = 4

15. Total monthly household income (including all sources of income):

taka

16. House possession :

House rented = 1, If yes  Taka

House owned = 2

Not owned, not rented and do not pay rent = 3

17. Which of the following items does the household own:

(Please circle the answer)

- |                |                |             |              |
|----------------|----------------|-------------|--------------|
| a. Khat        | b. Lep         | c. Tosak    | d. Hurricane |
| e. Watch/clock | f. Chair/table | g. Almirah  | h. Radio     |
| i. Television  | j. Bike        | k. Showcase | l. Cow       |
| m. Goat        | n. Electricity |             |              |

18. Form of fuel used for cooking:

Gas = 1 Firewood = 2 Cow dung = 3  
Kerosene = 4 Other = 5

Signature of the interviewer: \_\_\_\_\_

Code:

**Appendix 4**

**International Centre for Diarrhoeal Disease Research, Bangladesh  
Fish intervention on vitamin A status in children – a study in Mirpur**

**Dietary Intake Assessment by 24 h recall**

- 1. Study ID#: | | | |
- 2. Child Mapping ID#: | | | |
- 3. Name of child: \_\_\_\_\_
- 4. Household mapping ID#: | | | |
- 5. Camp \_\_\_\_\_ Camp code | |
- 6. Date of interview: | | | |  
DD MM YY
- 7. Respondent(s): 1= mother 2= father 3= others (relation to the child) \_\_\_\_\_

**I would like to talk now specifically about what you ate yesterday.**

- 8. Did you eat the normal amount of food yesterday?
  - Yes, same as usual..... 1 (Go to 9)
  - No, more than usual ..... 2
  - No, less than usual..... 3
  - Don't know ..... 9 (Go to 9)

8a. Why didn't you eat the normal amount of food? **[MORE ANSWERS POSSIBLE]**

\_\_\_\_\_

\_\_\_\_\_

\_\_\_\_\_

9. Now I would like you to remember exactly what you did and what foods you ate and any drinks you drunk yesterday. We will start with the first thing you did when you woke up yesterday. What time did you first eat something after you woke up yesterday?  
 What did you eat? **[PROBE FOR MAIN INGREDIENTS OF BHAJJIS, CURRIES, COMPOSITE DISHES]** When did you eat after that? etc. **[PROBE FOR SNACKS BETWEEN MEALS, PROBE FOR DRINKS (TEA WITH/WITHOUT MILK AND SUGAR, ALCOHOLIC DRINKS)]** **PROBE FOR BINP NUTRITION SUPPLEMENT AND ASK FOR FRACTIONS CONSUMED!!!**

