### **Food intake**

One 24 h dietary recall of all 550 children will be conducted as baseline information in order to assess habitual food and nutrient intakes at the group level. In addition, a semi-quantitative dietary assessment of vitamin A intake will be done in order to assess the risk of inadequate dietary vitamin A intake at the group level.

During the feeding trial, between *baseline* and *endpoint*, intakes of nutrients (vitamin A as well as energy, carbohydrate, protein, fat, iron, zinc and calcium) from foods not provided in the test meals will be calculated from biweekly food consumption surveys of the 180 children, using the 24 h recall method.

The results will be used to calculate the total daily intakes of nutrients in each treatment group during the feeding trial based on the following:

1) data from the food consumption surveys conducted between *baseline* and *endpoint* (mean of 4-5 dietary recalls) and 2) the amount of food given in the dishes (corrected for leftovers) and from the chemical analyses of duplicate samples of the dishes (please see below).

The total daily intakes of nutrients during feeding trial will be compared between treatment groups as well as with habitual food and nutrient intake.

The conduction of the 24 h recall method will be based on the method described by Gibson, 1990. The questionnaire is enclosed as Appendix 5.

The method used for conducting the semi-quantitative dietary assessment of vitamin A intake will be based on the method proposed by the International Vitamin A Consultative Group (IVACG) (Underwood *et al*, 1989). The questionnaire is enclosed as Appendix 4.

The health assistants will be trained, the questionnaires will be pre-tested, the health assistants will be checked in the field by supervisors and the filled out questionnaires will be checked daily.

A random check of 5% of the total number will be conducted in order to test the reliability of the 24 h dietary recalls, semi-quantitative assessment of vitamin A intake and morbidity questionnaires. This means that another person repeats the visit in the same household on the same day for 5% of the households. A quick comparison of the field assistant's questionnaire and the supervisor's questionnaire is done on the same day. At *baseline*, the field system may be adjusted to correct the faults.

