**24H-RECALL**

Hour	Food (List ingredients of composite dishes separate if possible)	Food code	Amount #	Household measure	HH measure code

Hour	Food (List ingredients of composite dishes separate if possible)	Food code	Amount #	Household measure	HH measure code

10. Did you take any other vitamin/mineral tablets yesterday?

- Yes ..... 1
- No..... 2 (Go to 11)
- Don't know..... 9 (Go to 11)

10a. Could you describe the vitamin/mineral tablets [**PROBE vitamin A, multivitamin; ask respondent to show package; show pictures/bottles to respondent**]

\_\_\_\_\_ |  |  |

\_\_\_\_\_

\_\_\_\_\_

\_\_\_\_\_

10b. During the last 2 weeks did the child take any vitamin/mineral tablets?

- Yes..... 1
- No..... 2 (Go to 11)
- Don't know..... 9 (Go to 11)

10c. Could you describe the vitamin/mineral tablets [**PROBE vitamin A, multivitamin; ask respondent to show package; show pictures/bottles to respondent**]

\_\_\_\_\_ |  |  |

\_\_\_\_\_

\_\_\_\_\_

\_\_\_\_\_

*Finally I would like to ask you some questions about the oil you normally use for cooking in the household.*

11. How many cups or small bottles of oil were used by the entire family for cooking purposes yesterday?

Number of cups  |  | **OR** | Number of bottles  |  |

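### As printed in English, the 24-hour recall form asks what the respondent ate rather than what the child ate, and its skip rule can bypass the only question on the child's supplements

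*Protocol*

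**What the plan says.** The Food intake section sets the purpose of the recall. At screening, "One 24 h dietary recall of all 550 children will be conducted as baseline information". During feeding, nutrient intakes "from foods not provided in the test meals will be calculated from biweekly food consumption surveys of the 180 children", again by 24-hour recall. The Data Analysis section enters nutrient intake during the study as a covariate in the analysis of covariance. The Compliance section says that mothers will be asked at the biweekly visits whether their children have taken supplements.

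The form is headed Appendix 4 (the Methods text cites it as Appendix 5). It opens with the child's name and ID numbers and lists who may answer: "Respondent(s): 1= mother 2= father 3= others (relation to the child"). The spoken part begins "I would like to talk now specifically about what you ate yesterday". Item 8 asks "Did you eat the normal amount of food yesterday", item 8a asks for the reason if not, and item 9 is the recall itself: "Now I would like you to remember exactly what you did and what foods you ate and any drinks you drunk yesterday". Item 10 continues "Did you take any other vitamin/mineral tablets yesterday". Item 10b then changes person: "During the last 2 weeks did the child take any vitamin/mineral tablets".

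**The concern.** The listed respondent is not the person being studied, and the script never says so. If an interviewer follows the printed English, the respondent describes his or her own day and the answer is filed under the child's ID. Such data could not be repaired at analysis, because nothing on the completed form would show whose diet was recorded.

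The supplement items carry a second fault. Vitamin A or multivitamin use during the trial could move serum retinol for reasons unrelated to the fish, and item 10b is the only item on this form about the child's supplements. The form does not put it to everyone.

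**Working it through.** The plan states no figure on this point, so the check is a comparison of texts.

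1. **Who answers.** Mother, father, or another person described by relation to the child. The child is not a listed respondent.

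2. **Whose intake is wanted.** The child's, by the Food intake, Compliance and Data Analysis sections.

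3. **Whom each item addresses.** The lead-in and items 8, 8a, 9 and 10 address *you*. Item 10b addresses the child. In items 10a and 10c *you* is the person describing the tablets, which is correct for a proxy.

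4. **Could *you* be shorthand for the child?** Not consistently, because item 10b switches within the same block. Item 9 also probes for alcoholic drinks, which fits an adult and not a child of 3 to 7 years. The same appendices can keep the two apart: the Perception of Mola form asks the mother about her child and has a separate section for the child. No instruction on Appendix 4 or in the Methods text tells staff to substitute the child.

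5. **The skip rule.** At item 10, both No and Don't know go to item 11. Item 10b is therefore reached only after Yes.
   - Taken literally: a respondent who took no tablet yesterday is never asked about the child. One who did take a tablet has it entered under the child's ID.
   - Taken charitably, with *you* meaning the child: a child who took nothing yesterday, but took a supplement earlier in the two weeks, is still not asked about.

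   The skip fault thus survives either reading of *you*.

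6. **Reach.** Baseline: 550 interviews. Trial: the Food intake section expects 4-5 recalls per child, so 180 × 4 = 720 to 180 × 5 = 900 if nobody drops out. Together 550 + 720 = 1,270 to 550 + 900 = 1,450 interviews use the form. This counts interviews exposed to the wording, not interviews misrecorded.

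7. **Where the data go.** Total daily intake is the recall of other foods plus the weighed test meal, which replaces one home meal. If a respondent described his or her own day, that person's midday meal could be added to the child's test meal. The recall also feeds the covariate, the comparison of intakes between groups, objective three, and the nutrient-intake part of objective five.

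8. **Item 12.** In English, the adult and child lines both carry the label < 18 y. The adult line must be wrong.

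**The case against.** The strongest reply is context. The form carries the child's name, the protocol speaks of one recall per child, and the interviewers are to be trained, supervised in the field and checked daily. A mother told that the visit concerns her child may well answer about the child. This stands: misrecording is a risk and not a certainty. A reader might infer that the mothers' diets would be stored as the children's throughout, and the documents do not support that. The safeguards do not remove the risk, however. None is directed at this wording, and the 5% repeat visit compares two copies of the same questionnaire, so both could agree on the wrong person.

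The second reply is that a Bangla version is likely to be what is read out. In the version sent to the Ethical Review Committee, the legible closing items show the same switch, from *you* for yesterday's tablets to the child for the last two weeks. The Bangla wording of the recall itself is not legible, so it cannot be said that the Bangla form has the fault throughout. No skip past the two-week item is visible there, though one may have been lost in extraction. The Bangla household item already separates adults from children.

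Third, the consequences are bounded. The semi-quantitative vitamin A form is a second baseline source for vitamin A foods and does not use this script, so the recall is not the only baseline record of those foods. That form is not repeated during feeding. Supplement use before enrolment is asked child by child on the household mapping form, so the eligibility check does not depend on Appendix 4.

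**Conclusion.** The English Appendix 4 is worded for the wrong person in its lead-in and in items 8, 8a, 9 and 10, and its skip rule withholds item 10b from anyone who does not answer Yes to item 10. Followed as printed, it could record the respondent's diet and tablets as the child's, and it undercuts the supplement check that the Compliance section promises.

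What is affected is the nutrient-intake covariate, the intake comparison between groups, objectives three and five, and the supplement check. A reader might infer a threat to the primary result. The documents do not support that: serum retinol is measured in the child's own blood, the sample size does not use intake data, and all three groups use the same form, so errors should fall on them roughly alike.

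Nor can a percentage be put on the error. The documents give no ratio of adult to child intake, no correlation between the two, and no indication of how many interviews would be read literally. The conclusion rests on the printed English text and, for Bangla, on the legible supplement items only. It merits correction, because the data are collected repeatedly and cannot be recovered afterwards.

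**What to change.** Change Appendix 4 before the pre-test that the memo accompanying the Bangla questionnaires says is still to come:

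- In the lead-in and items 8, 8a, 9 and 10, replace *you* with the child's name or *your child*, with the respondent answering as proxy.
- Ask item 10b whatever the answer to item 10, by redirecting No and Don't know at item 10 to item 10b.
- In item 9, drop the alcohol probe only. The probes for snacks, tea, milk and sugar can apply to a child and should stay.
- In the English item 12, correct the age label on the adult line.
- Compare the Bangla form with the corrected English item by item, above all the recall questions that could not be read here.

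The cost is rewording one form, with no extra visits, samples or staff.

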**24H-RECALL**

Hour	Food (List ingredients of composite dishes separate if possible)	Food code	Amount #	Household measure	HH measure code

Hour	Food (List ingredients of composite dishes separate if possible)	Food code	Amount #	Household measure	HH measure code

10. Did you take any other vitamin/mineral tablets yesterday?

- Yes ..... 1
- No..... 2 (Go to 11)
- Don't know..... 9 (Go to 11)

10a. Could you describe the vitamin/mineral tablets [**PROBE vitamin A, multivitamin; ask respondent to show package; show pictures/bottles to respondent**]

\_\_\_\_\_ |  |  |

\_\_\_\_\_

\_\_\_\_\_

\_\_\_\_\_

10b. During the last 2 weeks did the child take any vitamin/mineral tablets?

- Yes..... 1
- No..... 2 (Go to 11)
- Don't know..... 9 (Go to 11)

10c. Could you describe the vitamin/mineral tablets [**PROBE vitamin A, multivitamin; ask respondent to show package; show pictures/bottles to respondent**]

\_\_\_\_\_ |  |  |

\_\_\_\_\_

\_\_\_\_\_

\_\_\_\_\_

*Finally I would like to ask you some questions about the oil you normally use for cooking in the household.*

11. How many cups or small bottles of oil were used by the entire family for cooking purposes yesterday?

Number of cups  |  | **OR** | Number of bottles  |  |

**[IF RESPONDENT DOESN'T KNOW THEN FILL IN "99"; FRACTIONS ARE ALLOWED]**

12. How many people were eating in the household yesterday?

Number of adults (< 18 y)  |  |

Number of children (< 18 y)  |  |

**Appendix 5**  
**International Centre for Diarrhoeal Disease Research, Bangladesh**  
**Fish intervention on vitamin A status in children – a study in Mirpur**

**Semi-quantitative Dietary Assessment of Vitamin A**

1. Child Mapping ID#
2. Name of child
3.
4. Household mapping ID#      Camp code
5. Camp
6. Date of interview        
 DD MM YY
7. Respondent(s) 1= mother 2= father 3= others

FOOD CODE	FOOD NAME	CONSUMPTION DURING THE LAST 24 HOURS			OFFICE USE: FREQ/24 H SERVING SIZE			USUAL PATTERN: D = DAILY W= 1-6 DAYS/WEEK M= 1-3 DAYS/MONTHS N = NEVER				
		Morning Amount	Afternoon Amount	Evening Amount	S	M	L	D	W	M	N	
	Bengali name											
	GREEN LEAFY VEGETABLES:											
	Data shak											
	Lal shak											
	Pui shak											
	Kolmee shak											
	Mula shak											
	Palong shak											
	Helencha											
	Misti kumra shak											
	Lau shak											
	Misti allo shak											
	Sharisha leaves											
	Kanta naute											

Child's screening no.

FOOD CODE	FOOD NAME	CONSUMPTION DURING THE LAST 24 HOURS			OFFICE USE: FREQ/24 H SERVING SIZE			USUAL PATTERN: D = DAILY W= 1-6 DAYS/WEEK M= 1-3 DAYS/MONTHS N = NEVER				
		Morning Amount	Afternoon Amount	Evening Amount	S	M	L	D	W	M	N	
	Bengali name											
	VEGETABLES:											
	Data											
	Begun											
	Shim											
	Lal shim											
	Badha kopi											
	Borboti											
	Potol											
	Korola/Uchche											
	Chichinga											
	Misti kumra											
	Kakrol											
	Dherosh											
	Tomato (Kacha)											
	Kochu data/Lati											
	FRUITS:											
	Paka Pepe											
	Anarosh											
	Paka Tomato											

Child's screening no.

FOOD CODE	FOOD NAME	CONSUMPTION DURING THE LAST 24 HOURS			OFFICE USE: FREQ/24 H SERVING SIZE			USUAL PATTERN: D = DAILY W = 1-6 DAYS/WEEK M = 1-3 DAYS/MONTHS N = NEVER				
		Morning Amount	Afternoon Amount	Evening Amount	S	M	L	D	W	M	N	
	Bengali name											
	FISH:											
	Boal											
	Katla											
	Mohashole											
	Magur											
	Mola Mach											
	Dhela											
	MEAT and EGG:											
	Gorur Mangshaw											
	Murgee											
	Dim											
	MILK and MILK PRODUCT:											
	Gorur Dudh											
	Ghee											
	Other foods?											

Name of interviewer: \_\_\_\_\_

Code

18. Cold:

1 = Yes

2 = No

19. If yes, duration in days:

Days

**ALRI (Pneumonia):**

20. Able to drink:

1 = Yes

2 = No

21. Chest indrawing:

1 = Yes

2 = No

22. If yes, duration in days:

Days

23. Fast breathing

1 = Yes

2 = No

24. If yes, duration in days:

Days

25. Central cyanosis

1 = Yes

2 = No

26. If yes, duration in days:

Days

27. Fever:

1 = Yes

2 = No

28. If yes, duration in days:

Days

29. Measles:

1 = Yes

2 = No

30. If yes, duration in days:

Days

31. Night blindness:

1 = Yes

2 = No

32. If yes, duration in days:

Days

33. Vomiting:

1 = Yes

2 = No

34. If yes, duration in days:

Days

Child Mapping ID#     Study ID#

35. Ear discharge:

1 = Yes

2 = No

3 = one ears

4 = both ears

36. If yes, duration in days:

Days

37. Eye infection (conjunctivitis):

1 = Yes

2 = No

3 = one eye

4 = both eyes

38. If yes, duration in days:

Days

39. Angular stomatis:

1 = Yes

2 = No

40. If yes, duration in days:

Days

41. Referred / hospital visit required:

1 = Yes

2 = No

42. Diagnosis for which referred /hospital required: \_\_\_\_\_  
\_\_\_\_\_

43. Treatment given: \_\_\_\_\_  
\_\_\_\_\_  
\_\_\_\_\_

Date .....

Name of interviewer: .....

